6.3. Handling of Missing Data for Key Endpoints

6.3.1. Imputation for Missing Baseline Values

All available subjects in the ITT population have baseline values for both 6MWD and FVC. Hence, no baseline imputation is needed for these 2 key efficacy endpoints.

For the multi-component/multi-item endpoints (such as GSGC and MMT), a subject could be missing either specific items or the entire assessment. If the baseline value is partially missing (subject is missing only specific items at baseline), the average value using all subjects with non-missing values for that item across the 2 treatment groups combined will be used to replace the missing item score. If the baseline total score is completely missing, the average score using all subjects with non-missing total scores for the endpoint across the 2 treatment groups

combined will be used to replace the missing baseline total score. See Section 8.8.4 for the handling of missing baseline values for PROs including PROMIS instruments.

6.3.2. Imputation for Missing Post-baseline Values

For this study, subjects who permanently discontinued the assigned study drug are subsequently discontinued from the study. However, these subjects are required to return for the EOS/ET visit. Efficacy assessments collected at the EOS/ET visit will be used to replace the missing endpoint value at Week 52 in the ITT-LOCF population. That is, the last available observation will be carried forward to replace the missing value at Week 52 (see Section 6.1.4.2).

The MMRM analysis is the primary analysis for the primary endpoint (6MWD), and it will be performed as an ITT-OBS (observed cases) analysis. That is, all available, observed values will be used without imputation, and missing data at Week 52 are not replaced.

6.4. Handling of Intercurrent Events

Intercurrent events are defined as events that occur after treatment initiation and either preclude observation of the primary endpoint or affect its interpretation (eg, discontinuation of treatment, terminal events such as death, etc), per ICH E9 R1.

The potential intercurrent events for this study are listed in Table 5 together with the proposed strategy and handling of such events for the mixed-effect model repeated measures (MMRM) analysis and the analysis of covariance (ANCOVA).

Table 5: Accounting for Intercurrent Events

Intercurrent Event	Treatment Strategy for Handling Event	Handling of Event
Intervention for AEs, SAEs and IARs ^a ; Incorrect treatment assigned; Prespecified important major protocol deviations that can potentially affect the assessment of 6MWD.	Treatment policy strategy (based on ITT principle): 
 If subject continues in the study and dosing is resumed 	
For the ITT-OBS population: Value of interest (eg, 6MWD result observed at a given visit) will be used, regardless of whether the intercurrent event occurred. Note: No imputation will be performed for missing values at Week 52 (and other post-baseline visits). This is for the MMRM analysis.
 
For the ITT-LOCF population: Value of interest will be used, regardless of whether the intercurrent event occurred. Note: Missing values at Week 52 (and other post-baseline visits) will be imputed with the last available post-baseline assessment value. This is for the ANCOVA analysis.
 
Example: Compare “Treat A + Use of prohibited concomitant medication as needed” versus “Treat B + Use of prohibited concomitant medication as needed.”

	
 If subject permanently discontinues from study drug (and is withdrawn from the study) 	
For the ITT-OBS population: Observed value at time of discontinuation will be used. Note: No imputation will be performed for missing values at Week 52 and other post-baseline visits. Data after study discontinuation will be considered missing and will be handled by the MAR assumption in the MMRM analysis.
 
For the ITT-LOCF population: The last available assessment value will be used (regardless of whether the intercurrent event occurred). This setup is for the ANCOVA analysis.

Table 5: Accounting for Intercurrent Events (Continued)

Intercurrent Event	Treatment Strategy for Handling Event	Handling of Event
Withdrawn at subject’s own request (eg, subject withdrew consent); Withdrawn based on investigator’s opinion; Withdrawn for persistent noncompliance ^b ; Withdrawn due to SAEs or COVID-19 related reasons. Withdrawn due to IARs	Treatment policy strategy (based on ITT principle) Here, subject is permanently discontinued from study drug (and is withdrawn from the study).	
For the ITT-OBS population: The observed value available at time of discontinuation will be used. No imputation will be performed for missing values at Week 52 and other post-baseline visits. Data after study discontinuation will be considered missing and will be handled by the MAR assumption in the MMRM analysis;
 
For the ITT-LOCF population: The last available assessment value will be used, regardless of whether the intercurrent event occurred.
 
Note: This setup is for the ANCOVA analysis.

Abbreviations: 6MWT = 6-minute walk test; AE = adverse event; IAR = infusion-associated reaction; ITT = intent-to-treat; MAR = missing at random

Note: A subject who permanently discontinues study drug is subsequently withdrawn from this study.

^a Intervention for AEs and IARs includes concomitant medications, dose modifications, interruptions, or withdrawal.

^b Withdrawn for persistent noncompliance with study drug, study requirements, or failure to return to the study site for infusion visits. Eg, subject missed 5 or more infusions; or subject’s calculated compliance value < 80%.

6.4.1. Missing AE Attributes

Adverse events with missing attributes will be imputed with the worst possible outcome, for summary purposes. For example, if an AE is missing relationship to study drug, it will be imputed as being ‘related’ to the study drug; if an AE is missing the severity level, it will be imputed as being ‘severe.’

Nonetheless, in the data listings, the actual observed values will be reported. That is, if the response is missing, it will show as missing in the data listings.

6.4.2. Missing Start and Stop Dates for Prior and Concomitant Medication

Missing start and stop dates for prior and concomitant medications will be imputed in accordance with the rules described in Section 9.4.1.

6.4.3. Missing Start and Stop Dates for Adverse Events

Missing start and stop dates for AEs will be imputed in accordance with the rules described in Section 9.1.6.

7. CHARACTERISTICS OF STUDY POPULATION

7.1. Subject Disposition

For each analysis population (Screened, All Randomized, ITT, ITT-OBS, ITT-LOCF, mITT, Safety, PP, Completers, and PK), the study enrollment and completion status will be summarized by the number and percent of subjects who completed the study, who discontinued the study early for each treatment group, and for all subjects combined. The number of subjects who were randomized following rescreening will be included in the disposition table.

The number and percent of subjects, by the reason for discontinuing the study early, will also be presented for each treatment group and for all subjects combined. The categories classifying the subjects' study completion status are derived from the end of study electronic case report form (eCRF) page and include categories such as "Lost to Follow-Up," "Adverse Event," and "Death." The reasons for early study termination will likely provide some insight into how the trial was conducted and some understanding of the potential dropout pattern.

Study Completion/Termination Status:

The completion status of subjects at the end of the study will be categorized and summarized by treatment group with respect to the number of subjects who:

- Completed the study (based on the 'Yes' checked box on the eCRF)
- Discontinued the study prematurely

Note that the 'Yes' checked box on the eCRF does not necessarily indicate that the subject belongs to the Completers population. The Completers population is defined in Section 6.1.7. The reasons for early study termination will be summarized as recorded on the eCRF (eg, AE, protocol violation, administrative, lost to follow-up, death, COVID-19 related, etc).

7.2. Screen Failures

The number of subjects who failed screening will be presented in an individual subject data listing, which will include ERT status (ERT-naïve or ERT-experienced) and other demographic data.

7.3. Protocol Deviations

Protocol deviations data are collected and consolidated into a deviation log, and transferred to Amicus for review on an ongoing basis throughout the course of the study to identify trends and determine the type (eg, inclusion/exclusion criteria, study procedures) and the category (eg, minor or major) of each deviation. The number and percent of subjects with protocol deviations will be presented for each treatment group and summarized by deviation type (major or important). A listing of subjects with all protocol deviations (minor, major, and important) will be provided.

7.4. Demographic and Baseline Characteristics

Demographic and baseline characteristics will be summarized with descriptive statistics defined in Section 8.1 by treatment group for the ITT, mITT, and safety populations. Demographic and baseline characteristics to be presented include:

- Gender; race; ERT status (naïve or experienced); subjects using assistive devices at baseline; subjects with a history of falls (Yes, No); and subjects with a history of IARs (Yes, No) will be summarized by treatment group and overall using number and percentage as described in Section 8.1.
- The continuous variables height (cm), weight (kg), CK, Hex4, ALT, AST, and body mass index (BMI) (kg/m^2) will be summarized using descriptive statistics: number of observations (n), mean, standard deviation (SD), median, first quartile (Q1), third quartile (Q3), minimum, and maximum as described in Section 8.1.

Other baseline variables to be summarized will include:

- Age at informed consent date (in years), as a continuous variable;
 - Categorized as: ≥ 18 to < 35 years, ≥ 35 to < 50 years, ≥ 50 to < 65 years, ≥ 65 years
- Age at diagnosis (in years) as a continuous variable;
 - Categorized as: < 18 years, ≥ 18 to < 35 years, ≥ 35 to < 50 years, ≥ 50 years
- Age at first ERT dose in years (for subjects who are ERT-experienced only) as a continuous variable;
 - Categorized as: < 18 years, ≥ 18 to < 35 years, ≥ 35 to < 50 years, ≥ 50 years
- ERT duration (for ERT-experienced subjects) as a continuous variable, calculated as: $\text{ROUND}([\text{date of randomization} - \text{date of first dose of ERT}] / 365.25)$;
 - Categorized as: 2 to < 3 years, 3 to < 5 years, ≥ 5 years.

For partial dates involving age at diagnosis and age at first dose of ERT, missing Day will be imputed as '01,' and missing Month will be imputed as 'JANUARY.'

Other baseline characteristics include the baseline 6MWD (that is, the average of the 2 screening values), and the corresponding % predicted 6MWD, baseline FVC and other pulmonary function parameters, baseline motor function tests, muscle strength tests, and PROs.

The total number of subjects enrolled by country and by region will be presented by treatment group and overall. The 3 specified regions are: North/South America, Europe, and Asia Pacific. The demographic and baseline characteristics summary will also be presented by ERT status (naïve vs experienced).

The Pompe disease history information will be summarized for subjects who are ERT-naïve, ERT-experienced, have baseline 6MWD categorized as: 75 to < 150 m, 150 to < 400 m, and ≥ 400 m, based on the descriptive statistics defined in Section 8.1, for the ITT, and safety populations.

A listing of baseline data will be provided.

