6.2.3. Baseline Age

Calculation of subject’s age in years is based on the date of informed consent, using the following formula: Age (year) = FLOOR ([date of informed consent – date of birth] / 365.25), where the FLOOR () function returns the integer part of the result.

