8.5. Analysis of the Primary Efficacy Endpoint

8.5.1. Primary Efficacy Analysis

The primary efficacy endpoint (change from baseline to Week 52 in 6MWD) will be analyzed using an MMRM model to compare between treatment and control on the ITT-OBS population.

For this analysis, the dependent variable is the change from baseline to all post-baseline visits. Independent variables in the model are the fixed, categorical effects of treatment, time (ie, visit), treatment-by-time interaction, ERT status, and gender, as well as the fixed, continuous covariates of baseline 6MWD, baseline age, baseline weight, and baseline height. SAS PROC MIXED will be used for the analysis, with restricted maximum likelihood estimation (REML) and unstructured within-subject covariance structure. The Kenward-Roger approximation will be used to estimate denominator degrees of freedom and adjust standard errors for the tests of fixed effects. If this model fails to converge, a compound symmetry (CS) covariance structure will be used instead. The OBSMARGINS (OM) option in the LSMEANS statement will be specified to allow for the use of the observed marginal distributions of the categorical variable rather than assuming a balance among the levels of the categorical variable. The E option will also be specified to check for estimability of LS means.

All the relevant estimates from this model, including LS means, standard errors (SE), treatment differences in LS means, and the corresponding 95% CIs will be estimated for each time point. The main variable to be estimated (ie, the estimand) in the primary comparison is the difference between ATB200/AT2221 and alglucosidase alfa/placebo in mean change in 6MWD from baseline to Week 52, regardless of whether intercurrent events have occurred. The significance test will be based on the treatment comparison of LS means at Week 52 and a p-value will be presented for this time point only. Estimated LS means (\pm SE) for the change from baseline by treatment group will be plotted over time.

Exploratory Interaction Tests:

The study is not powered to detect any interaction. However, the following interactions will be explored.

Time-based interactions (ie, time-by-baseline 6MWD, time-by-baseline age, time-by-baseline weight, time-by-ERT status) will be examined separately (one at a time) in separate MMRM models to understand the changes over time.

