Similarly, treatment-by-covariate interactions (treatment-by-ERT status, treatment-by-baseline 6MWD, treatment-by-age, treatment-by-gender, treatment-by-weight, and treatment-by-height) will be explored. Each interaction term will be explored using a separate MMRM model that includes the full set of covariates of model terms (time, treatment-by-time interaction, gender, baseline 6MWD [continuous], baseline age [continuous], baseline weight [continuous], and baseline height [continuous]) as well as the added interaction term. The treatment-by-covariate interaction terms with a 2-sided $p < 0.10$ will be further examined clinically. Forest plots will be used to present the subgroups defined by the baseline covariates.

Secondary analyses of the primary endpoint and % predicted FVC (including supportive and sensitivity analyses) are described in Section 8.5.1.1 and Section 8.5.1.2. Analysis of the key secondary endpoints are described in Section 8.6, other secondary endpoints in Section 8.8, and subgroup analyses in Section 8.9. In all analyses involving the use of the LSMEANS, the OM option (as described above) will be used where applicable. If the LS means are not estimable with the OM option but they are without it, then the analysis without the OM option will be used. This will be footnoted accordingly.

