8.6. Analysis of the Key Secondary Endpoints

Key secondary endpoints will be analyzed according to the hierarchical order specified in Section [8.3.2](#) using a stepwise closed testing procedure to control the overall Type 1 error rate.

Each key secondary endpoint will be analyzed using an ANCOVA model on the ITT-LOCF population. The model will be adjusted for the baseline value (as a continuous covariate) and ERT status (ERT-naïve versus ERT-experienced), as well as baseline age, gender, baseline height, and baseline weight to compare between the 2 treatment groups. The OBSMARGINS (OM) option in the LSMEANS statement will be specified to allow for the use of the observed marginal distributions of the categorical variable rather than assuming a balance among the levels of the categorical variable. The E option will also be specified to check for estimability of LS means. If the LS means are not estimable with the OM option but they are without it, then the analysis without the OM option will be used.

All the relevant estimates from the ANCOVA (including LS means for each treatment group, LS mean difference, standard error of the estimate, 95% CI for the LS mean difference, and p-value for comparing between the 2 treatment groups) will be provided.

The treatment-by-covariate interactions (ie, treatment-by-ERT status, treatment-by-baseline value, treatment-by-age, treatment-by-gender, treatment-by-weight, and treatment-by-height) will be explored. Each interaction term will be explored using a separate ANCOVA model that includes the full set of covariates (ie, treatment, baseline value (as a continuous variable), ERT status, baseline age, gender, height, and weight) as well as the interaction term. Interaction terms with a 2-sided $p < 0.10$ will be further examined clinically. Forest plots will be used to present

the subgroups defined by the baseline covariates. A plot of the LS mean (\pm SE) change from baseline over time will be provided for each key secondary endpoint.

As a supportive analysis, each of the key secondary endpoints will be analyzed using an MMRM analysis on the ITT-OBS population. See further description in Section 8.5.1.1.

For the % predicted FVC, additional supportive and sensitivity analyses will be performed as specified in Section 8.5.1.1 and Section 8.5.1.2, respectively.

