8.9. Subgroup Analyses

Subgroup analyses by age group, gender, and race (using all available categories) will be performed for the primary endpoint and the change from baseline to Week 52 in % predicted FVC.

In addition, the following subgroups will be analyzed for the primary endpoint and the change from baseline to Week 52 in % predicted FVC, unless otherwise specified:

- ERT status (categorized as: ERT-experienced versus ERT-naïve)
This subgroup analysis will apply to the primary and key secondary endpoints, % predicted SVC, as well as for the overall adverse event (AE) overview table, summary of treatment-emergent AEs by system organ class and by preferred term, and PD endpoints.
- Baseline 6MWD (categorized as: 75 to < 150 meters, 150 to < 400 meters, ≥ 400 meters)
Note that for this subgroup analysis, categories may be collapsed depending on the actual number of subjects in each category, eg, 75 to < 150 meters and 150 to < 400 meters may be combined into 75 to < 400 meters.
- Baseline 6MWD < *median value*, baseline 6MWD ≥ *median value*
- Baseline FVC < *median value*, baseline FVC ≥ *median value*
- Regions (North/South America, Europe, Asia Pacific)
- ERT duration categorized as: 2 to < 3, 3 to < 5, and ≥ 5 years
- History of IARs (Yes, No)

All subgroup analysis results will be presented by forest plots. The p-values for the treatment-by-subgroup interactions will be presented together in a tabular form.

Note that subgroup analyses will not be performed if the size of the specified subgroup category is small and the analyses will not be meaningful.

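### Two SAP rules, if followed literally, give wrong exploratory ERT results: duration is rounded above its year bands, and the 6MWD interaction-model list omits ERT status and treatment

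*SAP*

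**What the plan says.** **ERT duration.** SAP 7.4 describes "ERT duration (for ERT-experienced subjects) as a continuous variable, calculated as" ROUND of (randomization date minus first ERT dose date)/365.25. No rounding unit is given. Directly beneath comes "Categorized as: 2 to < 3 years, 3 to < 5 years, ≥ 5 years". SAP 8.9 reuses the bands for 6MWD and % predicted FVC: "ERT duration categorized as: 2 to < 3, 3 to < 5, and ≥ 5 years". Neither section says whether the rounded or the unrounded value is banded. For age, SAP 6.2.3 names a different function and explains it: "where the FLOOR () function returns the integer part of the result".

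**Interaction models.** SAP 8.5.1 explores six treatment-by-covariate interactions for 6MWD, the first being treatment-by-ERT status. Each goes into a separate MMRM that is said to hold the "full set of covariates of model terms (time, treatment-by-time interaction, gender, baseline 6MWD [continuous], baseline age [continuous], baseline weight [continuous], and baseline height". ERT status is not in that list, and neither is the treatment main effect. The primary model in the same section has "treatment, time (ie, visit), treatment-by-time interaction, ERT status, and gender". The parallel list for the key secondary endpoints in 8.6 starts with treatment and baseline value and goes on to "ERT status, baseline age, gender, height, and weight) as well as the interaction term". The MMRM code in Appendix 3 also contains both terms and is offered as a template for the other MMRM analyses.

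**The concern.** Truncating to whole years leaves whole-year bands intact, because nobody crosses a whole-year boundary. Rounding to the nearest year does not: a subject with 2.6 years of ERT becomes 3 and moves up a band. If the rounded value is banded, the baseline table and the duration subgroup carry labels that do not describe the subjects in them.

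In the interaction model, a treatment-by-ERT-status term fitted without the ERT-status main effect has to carry that main effect as well. Its p-value then answers a mixed question: do naïve and experienced subjects differ at all, or does the treatment effect differ between them? SAP 8.5.1 sends terms with 2-sided p < 0.10 for clinical examination, so an ordinary prognostic difference could be read as a differential treatment effect.

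**Working it through.** The plan states no figure on either point. The design numbers used below do reproduce: with 66 and 33 subjects and effect size 0.7, the noncentrality is 0.7/√(1/66 + 1/33) = 3.28, which gives power 0.902 on 97 df, and 99/0.9 = 110.

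**1. Rounding**

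Assume that ROUND gives the nearest whole year and that the bands use the result.

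| Days | Years | Rounded | Intended band | Band after rounding |
|---|---|---|---|---|
| 731–913 | 2.0014–2.4997 | 2 | 2 to <3 | 2 to <3 |
| 914–1095 | 2.5024–2.9979 | 3 | 2 to <3 | 3 to <5 |
| 1096–1643 | 3.0007–4.4983 | 3 or 4 | 3 to <5 | 3 to <5 |
| 1644–1826 | 4.5010–4.9993 | 5 | 3 to <5 | ≥5 |

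The working cut-points are therefore 2.5 and 4.5 years. Of the day values in the first band, 182 of 365 move up; of those in the second, 183 of 731. These are shares of days, not of subjects.

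The share of subjects misbanded is P(2.5 ≤ D < 3) + P(4.5 ≤ D < 5). The documents give no distribution of D, so every line here is an assumption, applied to about 110 − 30 = 80 experienced subjects:

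- Uniform from 2 to 7, 9 or 14 years: 1/(upper limit − 2) = 20.0%, 14.3% or 8.3%, or about 16, 11 or 7 subjects.
- Two years plus an exponential with mean m = 2, 4 or 6: (e^(−0.5/m) − e^(−1/m)) + (e^(−2.5/m) − e^(−3/m)) = 23.6%, 16.7% or 12.6%.
- Normal with mean 8 and SD 3, truncated at 2: 5.3%.

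In the uniform cases the lowest band itself holds only about 16, 11 or 7 subjects, of whom one third (about 5, 4 or 2) are controls.

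**2. Interaction model without ERT status**

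Take 66/33 subjects, with 20/10 naïve (about 30 naïve, SAP 4.4) and 46/23 experienced, and no true interaction. An ERT difference δ common to both arms then gives the 2-df term the noncentrality

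λ = (20×46/66 + 10×23/33) × δ²/σ² = 20.91 × δ²/σ².

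*Range for δ.* SAP Appendix 1 gives matched alglucosidase alfa slopes of −0.65 and −2.15 points, a gap of 1.5 points. At 5.0 points = 20 to 40 m, that is 6 to 12 m. This is a weak proxy: the −0.65 comes from matches to five subjects, and those matches were themselves remaining on alglucosidase alfa. σ = 46.5 m is the Month 12 SD for Cohort 1 in Protocol Table 2.

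*Single visit.* λ = 0.35, 0.97 and 1.39 for δ = 6, 10 and 12 m. The term reaches p < 0.10 in 13.9%, 21.1% and 26.0% of trials.

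*Four visits (Weeks 12, 26, 38, 52).* Assume that the effect grows linearly to δ and that correlation is compound symmetric. The average effect is δ × (12+26+38+52)/(4×52) = 0.615δ, and the variance of a subject's mean is σ²(1+3ρ)/4.

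| ρ | 6 m | 10 m | 12 m |
|---|---|---|---|
| 0.5 | 12.4% | 16.7% | 19.7% |
| 0.7 | 11.9% | 15.4% | 17.8% |
| 0.8 | 11.7% | 14.9% | 17.1% |

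Simulation with gender and four continuous covariates agrees (for example 12.3%, 16.4% and 19.2% at ρ = 0.5). With ERT status in the model the rate is 9.7% to 10.2%. With no ERT difference, the model without it gives 9.9% to 10.0%.

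*A larger δ.* Protocol Table 2 shows Month 12 changes of +63.1 m (naïve, n = 5) and +42.2 m (experienced, n = 10), a gap of 20.9 m. In a single-visit simulation with σ = 28.6, 40 and 57 m (the ends being 20/0.7 and 40/0.7), the 2-df term is flagged in 91%, 67% and 42% of trials, against 9% to 11% with ERT status included. In the four-visit set-up with σ = 46.5 m, λ = 20.91 × (0.615 × 20.9)²/(46.5² × (1+3ρ)/4) = 2.56, 2.06 and 1.88 for ρ = 0.5, 0.7 and 0.8, which gives about 39%, 34% and 32%.

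**3. The other omissions**

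Treatment-by-time already spans the treatment main effect, so leaving treatment off the list does little harm. The other five treatment-by-covariate models lose only an adjustment for ERT status; their tests remain tests of interaction.

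**The case against.** The strongest reply is that the intent is plain elsewhere. SAP 7.4 calls duration continuous, a band from 2 to under 3 years would be an odd way to write the single integer 2, and the illustrative rows in Appendix 3 carry decimals. SAP 8.5.1 says that the whole set of terms is included, and the template code contains ERT status. A list that also drops treatment looks like loose shorthand rather than a program specification.

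Much of this stands: both faults are probably drafting slips, and a programmer who starts from Appendix 3 gets the right interaction test. But it does not settle the text. If duration is continuous, a ROUND without a unit conflicts with that. The Appendix 3 rows cannot serve as the derivation rule, because their key sets duration to 0 for naïve subjects while naïve rows show 2.4, 3.5 and 5.6 in that position. A programmer who works from the 8.5.1 list gets a different model from one who works from the appendix.

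The objection that the magnitudes depend on assumptions also stands. The misbanding range rests wholly on invented distributions, and the false-flag rate moves from about 12% to 91% with the chosen ERT difference, SD and model.

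A reader might infer more: that the main ERT comparisons are compromised, or that the duration covariate in the composite model of 8.7 is undefined. The documents do not support either. The primary model and the key secondary models list ERT status, and Appendix 3 partly defines the duration covariate.

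**Conclusion.** Wrong as written, but minor and confined to descriptive and exploratory results: the ERT-duration baseline table, the ERT-duration subgroup, and one of six treatment-by-covariate tests on 6MWD. Both effects depend on a literal reading.

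For rounding, the cut-points shift to 2.5 and 4.5 years if ROUND means whole years and the rounded value is banded. The share of subjects affected cannot be known from the documents; about 5% to 24% is a range over assumed distributions. The subgroup may not be run at all, since 8.9 says that "subgroup analyses will not be performed if the size of the specified subgroup category is small" and the analysis would not be meaningful.

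For the interaction test, the false-flag rate exceeds 10% whenever ERT status affects the change in 6MWD. It is about 12% to 20% for 6 to 12 m in the four-visit model. It is far higher at 20.9 m, but that gap rests on 5 and 10 subjects who all received ATB200/AT2221 in an open-label study. The consequence is limited, because 8.5.1 says the study is not powered for interactions and a flag leads only to clinical examination.

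The primary test, testing hierarchy, naïve/experienced subgroups and sample size are unaffected.

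**What to change.** - **SAP 7.4 and 8.9:** state that the bands are assigned from the unrounded quotient. Use rounding only for display, with a stated unit. Word the lowest band so that 24 calendar months of 730 days (730/365.25 = 1.9986 years) is classified. Do the same for any shorter duration that the Australia-specific part of inclusion criterion 5 may allow, since it does not restate the 24-month minimum.
- **SAP 8.5.1:** add both treatment and ERT status to the list in parentheses, so that it matches the primary model, 8.6 and the Appendix 3 code. Adding ERT status alone would still leave the lists different.

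The cost is two short text edits before database lock. Data collection, the primary analysis and the testing hierarchy do not change.
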